6.2.3 Concomitant acts and treatments

6.2.3.1 Collection of concomitant acts and treatments

Any concomitant medication or act at selection of the subject into the study must be reported on the source document and in the study Electronic Case Report Form at the initial visit and will be taken into consideration by the investigator deeming study eligibility.

Any modification on these treatments/acts during the study must be reported on the source document and in the study eCRF.

Use of any concomitant treatment will be recorded in the eCRF with the following information:

- Name of the treatment and unit strength;
- Indication for use of the treatment;
- Dose administered;
- Route of administration;
- Duration of treatment (start and stop date).

Use of any concomitant act will be recorded in the eCRF with the following information:

- Description of the act;
- Indication;
- Result;
- Duration (start and stop date).

6.2.3.2 Rescue treatment(s)

In case of adverse device effect affecting subject well-being, the investigator is authorized to interrupt the use of the investigational device and prescribe to the subject a rescue treatment.

The adverse event will be recorded in the subject's eCRF and source document, including details on rescue medication.

6.2.4 Number of investigational devices to be used

1 investigation device will be used per 1 subject.

6.3 STUDIED POPULATION

6.3.1 Inclusion criteria for subject selection

1. Healthy subjects
2. Gender: female and/or male.
3. Age: 18 – 45
4. Phototype I to IV according Fristzpatrick scale.
5. Healthy subject with normal physical examination results and a medical history compatible with the requirements of the study.
6. A healthy male or female subject with a medical diagnosis of mild to moderate facial acne vulgaris defined by at least 6 (six) inflammatory lesions, 12 (twelve) non-inflammatory lesions and no more than 2 (two) nodules (the nose is excluded for lesion count purposes).
7. Subject declares to avoid exposure to UV radiation (tanning booths, phototherapy and sun) on the face for at least three months prior to the selection visit and agrees to avoid it throughout the study.
8. Subject agrees not to apply any cosmetic, medical or aesthetic treatments outside the study protocol on the face for the duration of the study.
9. For female subjects:

Female subject not in childbearing status (tubal ligation, hysterectomy, bilateral oophorectomy),
or

Female subjects of childbearing potential who, in the opinion of the investigator, are using a reliable method of contraception (pill or contraceptive patch, IUD, implant or vaginal ring, condoms) for at least one month prior to the screening visit. Subject willing to continue using contraception during the study and one month after the end of the study.

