6.3.5 Enrolment procedure

Subjects will be pre-selected by phone from Eurofins Dermscan Pharmascan data base, according to inclusion and exclusion study criteria. This data base is constituted from registration files of people wishing to participate in clinical studies at Eurofins Dermscan Pharmascan.

Advertisement will be placed in Eurofins Dermscan Pharmascan website.

Pre-selected subjects will come to the site for consent form signature on D0 visit and then will be included if eligible according to inclusion and exclusion criteria. The informed consent process is explained in section 13.

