6.4.1.2 Study schedule

Visit 1: D0

- Subjects will come to the investigational site with their completed diary.
- Information of the subjects on study aims and schedule.
- Signature of consent form in two copies by the subject and the investigator in charge of the screening visit.
- Medical examination for verification of subject's health state, collection of previous medical history, previous and actual treatments.
- A urinary pregnancy test will be performed for women with childbearing potential.
- Checking of inclusion and exclusion criteria.
- Distribution to the subjects of accompany treatment with the instructions of use.
- Colorface standardized photos will be taken by the Technician.
- Acne lesions will be counted by the Investigator.
- Distribution of the ID card and diary so they can note the adverse events and concomitant treatments / acts.

Visit 2, 3 and 4: D15, D36 and D57

- Subjects will come to the investigational site with their completed diary.
- Checking of exclusion criteria.
- Colorface standardized photos will be taken by the Technician.
- Acne lesions will be counted by the Investigator.
- Peeling act will be performed by the Investigator.
- Record of AE and concomitant treatments.

Visit 5: D78

- Subjects will come to the investigational site with their completed diary.
- Checking of exclusion criteria.
- Colorface standardized photos will be taken by the Technician.
- Acne lesions will be counted by the Investigator.
- Subjective questionnaire.
- Scoring of Patient global assessment.
- Score of Investigator global assessment.
- Record of AE and concomitant treatments.

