6.4.2 Description of effectiveness parameters

6.4.2.1 Counting of the acne lesions

Investigator will perform acne lesions counting (front, 2 cheeks, the chin above the jaw line (excluding the nose)) using both visual observation and palpation on each visit (baseline, D15, D36, D57 and D78). Total lesions will be defined as the sum of inflammatory lesions (papules, pustules), non-inflammatory lesions (whiteheads and blackheads) and other acne lesions (nodules).

The change of the number of acne lesions from baseline will be calculated on each visit.

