7.7 MANAGEMENT OF BIAS

Not applicable.

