13.2 PROCESS FOR SUBJECT'S INFORMATION AND CONSENT OBTAINING ON INVESTIGATIONAL SITE

A first information about the study aims and investigational device will be given by phone by the centre recruitment team (see section 6.3.5; phone call lasts approximately 15 minutes).

At screening visit (at least 24h before D0 visit), the investigator or delegates will again inform the subject about the study aims and constraints as well as the investigational device and will give him two paper copies of the informed consent form. After a reflexion time of 20 minutes on site and after all further questions are resolved, if the subject agrees to participate to the study, he will be asked to date and sign the informed consent in two original copies.

14- ADVERSE EVENTS, ADVERSE DEVICE EFFECTS AND DEVICE DEFICIENCIES

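### One D0 lesion count appears both to admit subjects and to serve as the primary baseline, so part of any fall from D0 may be regression to the mean

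*Combined protocol and SAP*

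**What the plan says.** Criterion 6 in section 6.3.1 requires mild to moderate facial acne "defined by at least 6 (six) inflammatory lesions, 12 (twelve) non-inflammatory lesions and no more than 2 (two) nodules". These are lower limits on both main lesion types. The only upper limit is on nodules.

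On timing, section 6.3.5 states: "Pre-selected subjects will come to the site for consent form signature on D0 visit and then will be included if eligible". The D0 visit in 6.4.1.2 contains both steps: "Checking of inclusion and exclusion criteria" and, later in the same list, "Acne lesions will be counted by the Investigator". Neither flow chart shows an earlier count. Section 13.2 does refer to an earlier contact ("At screening visit (at least 24h before D0 visit"), but uses it for information and consent and assigns it no lesion count.

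On the endpoint, section 6.4.2.1 schedules counts "on each visit (baseline, D15, D36, D57 and D78" and adds: "The change of the number of acne lesions from baseline will be calculated on each visit". Section 7.2.2 builds the model contrast from the first measurement, which is D0.

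The study is open, single-arm and not randomised (6.1.1, 6.3.6). Section 7.7, on management of bias, reads "Not applicable", and so does 6.1.2. Section 6.4.5 names no factor that could compromise interpretation, and 7.8 identifies no confounder. Regression to the mean is not mentioned.

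**The concern.** A subject's count varies from visit to visit, through counting error and through lesions appearing and clearing. A lower limit applied to one count admits some people whose count was high that day and turns away some whose count was low. The admitted group's D0 mean then overstates its usual level, and later counts drift down with no treatment at all. A second, unselected baseline or a control arm would expose this drift, and the plan has neither.

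The synopsis calls the study confirmatory and 7.5 sets no pass/fail criterion, so a significant fall from D0 could be reported as device performance. The mechanism is separate from the timing of the first peel: it would operate even if the peel were applied at D0.

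**Working it through.** **Plan's own figures.** The only planning figure is 33 subjects for 30 evaluable, an allowance of 3/33 = 9.1% for losses. No expected count, SD, effect size or power is stated, so the size of the effect cannot be derived from the documents. Everything below on size rests on assumptions.

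**Inputs from the plan.** Entry limits 6 and 12 (6.3.1); change in total count from D0 (6.4.2.1, 7.2.2); n = 30 (6.1.6); two-sided 5% (7.3), hence 2.5% in the direction of a fall.

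**Assumptions.** Log-normal subject means with between-subject CV 0.5; extra within-subject fluctuation with CV 0 to 0.3; Poisson counts at each visit; no treatment effect; a paired test at one follow-up visit.

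**Simulation.** Draw D0 and follow-up counts, keep subjects with D0 counts of at least 6 and 12, and average the change in the total:

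| Candidate mean (inflammatory + non-inflammatory) | D0 mean of those admitted | Mean change | Fall | Chance of a significant fall |
|---|---|---|---|---|
| 8+16 | 30.7–32.4 | −1.9 to −3.6 | 6–11% | 28–34% |
| 10+20 | 35.0–36.7 | −1.3 to −2.6 | 4–7% | 13–17% |
| 15+30 | 47.3–48.8 | −0.5 to −1.3 | 1–3% | about 5% |
| 20+40 | – | – | 1% or less | near nominal |

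For example, 1.9/30.7 = 6.2% and 3.6/32.4 = 11.1%.

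**Second model.** With a correlation of 0.4 between the two lesion types, the results at 10+20 are a fall of 3–7% and a chance of 11–17%. At its lower end the standardised change is 0.14. The noncentrality is then 0.14 × √30 = 0.77, against a critical t of about 2.05 on 29 df, in line with the simulated 11%.

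**Analytic check.** For a normal total truncated at 6 + 12 = 18, the expected fall is (1 − ρ) × SD × λ, where λ is the inverse Mills ratio at (18 − mean)/SD. With mean 30 and SD 15, λ = 0.37. For ρ = 0.9 to 0.6 the fall is 0.55 to 2.21 lesions, or 1.6–6.2% of the observed baseline. With mean 45 and SD 20 it is 0.7–2.9%. The order of magnitude agrees.

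**Would a separate baseline help?** Two cases differ.

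- *Independent later count as reference.* Given the subject's usual level, the mean change returns to about 0 (−0.02 to +0.02 lesions), and the two-sided rejection rate is 4.0–5.4%.
- *Recount on the same day.* Treat the Poisson draw as lesions actually present and add an assumed 10% miscount. At 8+16 without extra fluctuation, the fall only drops from 2.1 to 1.9 lesions. Over the range of fluctuation, the chance of a false significant fall remains 24–32%.

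All these chances are for one visit. The plan tests four post-baseline visits without adjustment (7.9), so the chance of at least one false fall is higher.

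**The case against.** **The premise is inferred.** No sentence says that the D0 count decides eligibility. The D0 list puts the criteria check before the count, 13.2 mentions an earlier screening visit, and 6.4.1.1 separates the practitioners who include subjects from the independent live evaluators. This stands as a caution. Against it, criterion 6 cannot be applied without a count, and the schedule offers only the one at D0.

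**The size may be trivial.** This also stands. Criterion 6 covers mild to moderate acne with no upper limit on inflammatory or non-inflammatory lesions, so nothing shows that recruits sit near 6 and 12. The 8+16 case admits only 38–43% of candidates; at 15+30, 80–87% are admitted and the artefact is small. However, the stated target is mild acne (1.1, 2.6), so the lower cases cannot be dismissed.

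**A recount at D0 or a day apart sees mostly the same lesions.** This is right, as the same-day calculation shows. A separate baseline count alone is not enough.

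**Stronger readings that the documents do not support.** A reader might infer that the lesion count is the only evidence of efficacy. It is the only primary endpoint, but 6.1.3.2 also lists pore and texture analysis, photographs, and global assessments by investigator and patient. A reader might also infer that investigators will round borderline counts up to the limits. That is possible, but nothing in the documents shows it and it is not part of the figures above.

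**Conclusion.** The concern holds in a limited form. As scheduled, one D0 count appears to serve both purposes, and with no control arm part of any fall from D0 may be regression to the mean. The plan neither prevents nor acknowledges this.

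Under the assumptions stated, the artefact ranges from 1% or less of baseline (candidates averaging 20+40) to 6–11% (8+16). The documents do not say where the recruits will lie. It would be wrong to conclude that a fall of a given size is guaranteed, or that the whole of an observed fall would be artefact: both would require a lesion distribution that the plan does not give. The point merits correction because the remedy is cheap, not because the bias is shown to be large.

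**What to change.** 1. **Separate the two counts.** Use one count for eligibility and another as baseline. Have the baseline count made by the independent live evaluator of 6.4.1.1, without sight of the eligibility count, and exclude no one on it. Reconcile 6.3.5, 6.4.1.2 and 13.2 on whether a screening visit precedes D0. This removes selection on counting error, and on any rounding at the limits, but not true lesion fluctuation.
2. **Use the D15 count as a second reference.** In 7.2, pre-specify contrasts of D36, D57 and D78 against D15 from the same mixed model, as a sensitivity analysis. Section 7.2.2 words that model for variables obtained from devices, so state that it also covers the lesion count. D15 is not an entry count, and 6.4.1.2 lists it ahead of the peel; say explicitly that it is made before the peel, as 6.4.2.2 already does for the photographs. Two limits should be stated: the accompanying cosmetics are given out at D0, so D15 is not treatment-free; and fluctuation slower than about two weeks would leave some regression after D15.
3. **Rewrite 7.7.** Replace the present entry with these measures, and report residual regression to the mean as a limitation.

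Cost: one extra lesion count of a few minutes per subject, by staff already named, and one extra set of contrasts from visits already scheduled. Some baselines will fall below 6 or 12, which is the expected result of separating the counts.

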6.3.2 Exclusion criteria for subject selection

1. Pregnant or nursing woman or planning a pregnancy during the study.
2. Subject who had been deprived of their freedom by administrative or legal decision or who is under guardianship.
3. Subject in a social or sanitary establishment.
4. Subject participating to another clinical research or being in an exclusion period for a previous study.
5. Intensive exposure to sunlight or UV-rays within the previous 3 months and foreseen during the study.
6. Subject with any skin or systemic disease (acute and/or chronic), in the previous year, likely to interfere with the measured parameters or to put the subject to an undue risk.
7. Subject having history of allergy or hypersensitivity to one of the components of the tested device.
8. Subject receiving any treatment that, in the opinion of the clinical investigator, may interfere with test results or put the subject to undue risk.
9. Subjects on topical or oral treatments (such as Benzoyl Peroxide, Retinoic Acid, Isotretinoine) that did not stop the treatment 30 days before their first peel (risk of over-peeling).
10. Subjects with known salicylism or related medical indications.

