6.2.1.3 Precautions for use

For external use only and for use on a limited area, due to the presence of Salicylic Acid. For adults only.

- Skin preparation is recommended 15 days before the first peel.
- Must only be used by trained healthcare professionals. Required knowledge of complications associated with the application of medical devices and how to react is necessary.
- Always use protective gloves during the procedure and clean the glass cup carefully between each peel session. Cotton buds should be disposed of after each use.
- Do not use alcohol or acetone-based cleanser.
- Avoid the lip area and nasolabial folds. Do not swallow.
- Avoid eyes and mucous membranes: in the event of accidental contact, rinse thoroughly with water, and use a saline solution.
- Avoid sun exposure and use sun protection (K Ceutic or Sun Ceutic 50+) for 4 weeks after the treatment and in-between treatments.
- Keep out of the reach of children.
- In case of alteration in the product's appearance, do not use the medical device.
- Protocol variations should be based on assessment of patient skin type, treatment tolerance and desired results.
- Do not apply on a large area or other areas of the body to avoid a high absorption of Salicylic Acid.
- Never hold the medical device above the patient to avoid accidental spillage.
- If an allergic reaction is considered likely, apply the product to a 1 cm² sized area behind the ear, following the exact same protocol. If no unusual reaction is observed within 72 hours, the facial peel can go ahead.

The practitioners are asked to refer to the last version available of IFU/IB.

6.2.2 List of other medical device or medication to be used during the clinical investigation

No other medical device or medication is planned to be used according to the CIP. However the associated cosmetic products are to be used during the investigation.

Accompanying products are commercially available products developed by DERMOSCIENCES LTD. They are used to prepare and protect the skin during the peeling procedures and to maintain the effect of the peeling.

Foamer 15 (15 % glycolic acid foamer):

- Use as a pre-peel: Cleanse the face with 4 squeezes spread over the whole face, rinse thoroughly after 2 minutes or as soon as the first tingling appears and dry.
- Use at home: Apply a small amount of foam to the clean and dry face.

Massage and rinse with water after two minutes or as soon as you start to feel tingling.

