- Precautions: You may feel a tingling sensation. If discomfort occurs, reduce the frequency of use.
- Do not apply to irritated or damaged skin, or to the eyes and mucous membranes.

Avoid exposure to the sun.

Hyal Ceutic (Intense moisturizing cream):

- Use: Apply when skin needs moisturising, all over the face during the day as required.
- Precautions for use: Avoid contact with eyes and mucous membranes. In case of contact, rinse with plenty of water. Do not apply to open wounds.

Sun Ceutic teintée (SPF 50+ product, slightly tinted):

- Use: Every morning, apply evenly to the face, neck and décolleté 10 minutes before sun exposure. Reapply frequently.
- Precautions for use: Do not apply to irritated or damaged skin, or to the eyes and mucous membranes. In case of contact, rinse with plenty of water. Avoid prolonged exposure to the sun, even with the cream.

DUAL+ (Night cream):

- Use: Apply in the evening to the full face focusing especially on the areas of concern. Increase frequency progressively, up to 2 times per day.

PRECAUTIONS You may experience a tingling sensation, redness and slight desquamation. In case of discomfort, reduce the frequency of use.

DERMOSCIENCES FRANCE	Medical Device CIP # 22E2387	Final version 1.0 Date: 16.08.2022	Confidential Page 26/49
-------------------------	---------------------------------	---------------------------------------	----------------------------

Do not apply to irritated or broken skin. Do not combine this product with other retinol-based products. Avoid direct contact with eyes and mucous membranes.

During use, avoid exposure to sunlight without high SPF protection.

Not recommended for sensitive and/or very dry skin.

NB: All these cosmetic products are in the market

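### Exclusion 7 names allergy to components of the tested device only, although subjects are also given three facial cosmetics that are not in the device kit (minor, cheap safety improvement)

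*Combined protocol and SAP*

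**What the plan says.** Exclusion 7 in section 6.3.2 rules out a "Subject having history of allergy or hypersensitivity to one of the components of the tested device". The synopsis has the same wording.

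Section 6.2.2 says that no other device or medication is planned, then adds: "However the associated cosmetic products are to be used during the investigation". It lists four products: Foamer 15, Hyal Ceutic, Sun Ceutic teintée and DUAL+. The directions for the last three are:

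- Sun Ceutic: "Every morning, apply evenly to the face".
- Hyal Ceutic: "Apply when skin needs moisturising, all over the face during the day as required".
- DUAL+: "Apply in the evening to the full face focusing especially on the areas of concern", with frequency raised gradually to at most twice a day. The DUAL+ precautions include "You may experience a tingling sensation, redness and slight desquamation", "In case of discomfort, reduce the frequency of use" and "Not recommended for sensitive and/or very dry skin".

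Section 2.1 gives the kit contents: the peel, Foamer 15, cotton buds, a cup and the instructions. Section 6.4.1.2 has the accompanying products handed out at D0 with their instructions for use. In that visit list the medical examination, history and check of criteria come first. Section 4.5 names the entry criteria as the means by which risk is mitigated.

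**The concern.** Section 4.2 accepts that any topical product carries a risk of allergy to one of its components, and exclusion 7 is how the plan acts on that for the peel. The same reasoning applies to creams that the plan itself supplies for the face, two of them with daily directions. As written, a subject with a known allergy to an ingredient found only in one of those creams meets no explicit exclusion and can be handed the product at D0.

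What is at stake is an avoidable skin reaction, probably mild, in an identifiable subject. This is a matter of subject protection. It does not bear on the validity of the lesion-count analysis.

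**Working it through.** The plan states no figure on this point, so the check is a comparison of texts with simple counts.

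**1. Which supplied products are outside the kit?** Section 6.2.2 lists 4 accompanying products. Section 2.1 places 1 of them, Foamer 15, in the kit; it is treated here as part of the tested device. 4 − 1 = 3 remain: Hyal Ceutic, Sun Ceutic and DUAL+. One of these (Hyal Ceutic) is used as needed, so 3 − 1 = 2 have daily directions.

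**2. Does any entry criterion name them?** Section 6.3.1 has 9 inclusion criteria and section 6.3.2 has 10 exclusion criteria: 9 + 10 = 19. Exclusion 7 is the only one about allergy, and it stops at the tested device. Criteria naming allergy to an accompanying product: 0 of 19.

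**3. Would a general criterion catch the subject anyway?**

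- Inclusion 5 asks for a medical history compatible with the study. An investigator could apply it, but it does not prompt the question.
- Exclusion 6 requires a skin or systemic disease in the previous year. An older allergic reaction may fall outside that window.
- Exclusion 8 concerns treatments being received, so it does not apply.

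**4. Do the ingredients overlap?** Exclusion 7 works by component, so an allergy to an ingredient shared with the peel is already excluded. For the peel the documents give salicylic acid (20%), mandelic acid (5%), citric acid (5%) and an alcohol-water solvent (sections 2.1 and 4.6). No ingredient list is given for the three cosmetics. The one hint is the advice not to combine DUAL+ with other retinol-based products, which suggests that it is retinol-based itself. That does not settle the degree of overlap.

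**5. How many subjects, and when?** The products go to included subjects, 33 planned. The first peel is at D15 ± 1, so the products are in subjects' hands 15 − 1 = 14 to 15 + 1 = 16 days earlier. The documents do not state how long each product is used after that, or how common such allergies are, so no number of affected subjects can be given.

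**The case against.** The case against giving this weight is a good one. The products are marketed cosmetics, and the reactions listed for DUAL+ are mild. A dermatologist takes the history before anything is handed out, and inclusion 5 lets that dermatologist refuse the subject. Instructions for use come with the products, although the leaflets are not in the documents and their warnings cannot be judged. DUAL+ is started gradually. Section 6.2.1.3 names K Ceutic beside Sun Ceutic for sun protection. All of this stands and keeps the point minor. It does not close the gap: none of these safeguards requires anyone to ask about the cosmetics before exposure, and the behind-the-ear test in section 6.2.1.3 is described for the peel.

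A reader might draw three stronger conclusions that the documents do not support.

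- *That three of the four products fall outside exclusion 7.* The criterion is written by component and overlap cannot be checked. What can be shown is that three products are not named.
- *That the DUAL+ skin-type precaution calls for a new exclusion of sensitive or very dry skin.* It is a not-recommended note on an accessory cream, not a contraindication to the peel. Such a criterion would narrow a device study on account of that cream and would still rest on investigator judgment. Nor would it preserve a uniform regimen: Hyal Ceutic use, DUAL+ frequency and the number of peel layers (section 6.2.1.2) already vary by subject.
- *That the gap harms power, error rates or the attribution of reactions.* Nothing in the plan shows this.

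**Conclusion.** The point holds as a minor safety improvement. Exclusion 7 is narrower than the set of products that the plan puts on subjects' faces: three supplied cosmetics are not named, and 0 of 19 criteria mention allergy to them. Only the general wording of inclusion 5 and exclusion 6 would otherwise catch a subject with such an allergy.

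This rests on two assumptions. Foamer 15 is taken as covered because it is in the kit. At least one of the three cosmetics is taken to contain an ingredient that the device does not, which is plausible but cannot be confirmed from the documents. If every ingredient were shared, the change would be redundant but harmless.

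**What to change.** In the synopsis and in section 6.3.2, let exclusion 7 end with: *components of the tested device or of any accompanying product used in the CIP*. This wording also takes in Foamer 15, and K Ceutic if it is used.

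The cost is one phrase in two places and possibly a few more screen failures. No visit or procedure is added: phone pre-selection already follows the criteria (section 6.3.5), and the D0 history and criteria check are already listed before distribution. The site needs the ingredient lists of the accompanying products at hand to apply the criterion.

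Optional, and not part of this fix: the sponsor may allow the investigator to leave out DUAL+ at D0 for a subject with sensitive or very dry skin, and to record that.

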Exclusion criteria:	
1. Pregnant or nursing woman or planning a pregnancy during the study.2. Subject who had been deprived of their freedom by administrative or legal decision or who is under guardianship.3. Subject in a social or sanitary establishment.4. Subject participating to another clinical research or being in an exclusion period for a previous study.5. Intensive exposure to sunlight or UV-rays within the previous 3 months and foreseen during the study.6. Subject with any skin or systemic disease (acute and/or chronic), in the previous year, likely to interfere with the measured parameters or to put the subject to an undue risk.7. Subject having history of allergy or hypersensitivity to one of the components of the tested device.8. Subject receiving any treatment that, in the opinion of the clinical investigator, may interfere with test results or put the subject to undue risk.9. Subjects on topical or oral treatments (such as Benzoyl Peroxide, Retinoic Acid, Isotretinoine) that did not stop the treatment 30 days before their first peel (risk of over-peeling).10. Subjects with known salicylism or related medical indications.

DERMOSCIENCES FRANCE	Medical Device CIP # 22E2387	Final version 1.0 Date: 16.08.2022	Confidential Page 12/49
-------------------------	---------------------------------	---------------------------------------	----------------------------

Investigational device: Name / code Galenic form Dosage and duration	CRYSTAL PEEL Liquid 3 applications performed by the dermatologist: 2.5 ml of Crystal Peel applied with a cotton swab on the face. Apply up to 3 coats, waiting 1 minute between each coat. Leave the last coat on for up to 5 minutes, while observing the skin's reaction.
Administration route	Topical administration
Endpoints:	
Primary endpoint: Comparison of the change from baseline of total sum of lesions on each visit.
 
Secondary endpoints: Pores and texture analysis Visual effect - photographs Investigator Global Assessment score Patient Global Assessment score Local and overall tolerance of the Crystal Peel Subject's self-evaluation on D78 using a questionnaire. Adverse events number

Study Procedures:	D0, D15 (peeling act), D36 (peeling act), D57 (peeling act), D78

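### Exclusion 9 counts the 30 days off acne treatment to the first peel, so only an implied 14 to 16 days protects the D0 lesion count from which the primary change is measured

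*Combined protocol and SAP*

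**What the plan says.** Exclusion 9 in section 6.3.2, repeated in the synopsis, excludes subjects on topical or oral treatments such as benzoyl peroxide, retinoic acid or isotretinoin who "did not stop the treatment 30 days before their first peel". The reason given is the risk of over-peeling, so it is a safety rule.

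The synopsis sets the visits as "D0, D15 (peeling act), D36 (peeling act), D57 (peeling act), D78", and the schedule in section 6.1.4 allows ±1 day around D15. Section 6.4.2.1 has lesions counted at baseline and at each later visit, and states: "The change of the number of acne lesions from baseline will be calculated on each visit". Section 7.2.2 builds the model contrast against the first measurement, which is D0.

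Other entry rules touch on earlier treatment or on the baseline count:

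- Inclusion 5 asks for "a medical history compatible with the requirements of the study".
- Exclusion 8 covers a "Subject receiving any treatment that, in the opinion of the clinical investigator, may interfere with test results".
- Inclusion 6 requires "at least 6 (six) inflammatory lesions, 12 (twelve) non-inflammatory lesions".
- Inclusion 8 bars outside facial treatments, but only while the study runs.
- D0 includes a history of previous and current treatments (section 6.4.1.2).

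Two other minimum intervals in section 6.3.1 are tied to study entry. Facial UV avoidance applies "on the face for at least three months prior to the selection visit", and contraception must have been in use "for at least one month prior to the screening visit".

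**The concern.** The 30 days are counted to one visit and the primary change starts from another, about two weeks earlier. A subject can satisfy exclusion 9 in full and still have stopped acne treatment only about a fortnight before the baseline count.

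If lesion counts are still moving at D0 because of that withdrawal, the movement enters the change from baseline. The study is open, monocentric and intra-individual (synopsis; section 6.1.1), with no concurrent control to show what the counts would have done without the regimen. No count before D0 is scheduled that would show whether the baseline is stable. Sections 7.7 and 7.8 provide no measure against bias and identify no confounder.

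There is also a practical consequence. Borderline eligibility depends on a visit that has not yet happened. A subject 14 days off treatment at D0 complies if peeled on D16, but not on D14 or D15. Exclusion criteria are rechecked at that visit, and section 6.1.6 does not allow replacement.

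**Working it through.** **Inputs from the plan**

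- 30 days, counted back from the first peel (section 6.3.2).
- First peel on D14, D15 or D16 (section 6.1.4).
- Primary change measured from D0 (sections 6.4.2.1 and 7.2.2).
- 30 evaluable subjects (section 6.1.6).
- Minimum eligible count 6 + 12 = 18 lesions (inclusion 6).
- Enrolment about 6 weeks, 78 days per subject, 17 weeks in total (sections 6.3.7 and 6.3.9).

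**Minimum time off treatment at D0 under the current rule** = 30 − day of first peel

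- Peel on D14: 30 − 14 = 16 days
- Peel on D15: 30 − 15 = 15 days
- Peel on D16: 30 − 16 = 14 days

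The implied floor at baseline is 14 to 16 days, about half of the 30. It is a permitted minimum, not the typical case.

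**Time off treatment at the first peel if the 30 days run to D0** = 30 + day of first peel, which gives 30 + 14 = 44 to 30 + 16 = 46 days. The over-peeling requirement is still met.

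**Extra wait for a subject at the current minimum**: 30 − 16 = 14 to 30 − 14 = 16 days.

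**Possible shift in the mean change (illustration).** The documents give neither the number of recent stoppers, k, nor the drift per subject after D0, d. Assume k = 1 to 5 and d = 2 to 5 lesions. Shift = k × d / 30:

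- Low end: 1 × 2 / 30 = 0.07 lesion; 0.067 / 18 = 0.4% of the minimum eligible count
- High end: 5 × 5 / 30 = 0.83 lesion; 0.833 / 18 = 4.6%
- No affected subjects: 0

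**Cost of a sensitivity analysis omitting k of 30 subjects.** At the same SD, the 95% CI width ratio is [t(n−1)/√n] / [t(29)/√30]:

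- n = 29: 1.019
- n = 27: 1.059
- n = 25: 1.105

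The interval widens by about 2 to 11%.

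**Slack in the timetable**: 78 / 7 = 11.1 weeks, and 6 + 11.1 = 17.1 weeks against 17 planned. A wait of 14 to 16 days is 14/42 = 33% to 16/42 = 38% of the enrolment window.

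**The case against.** Tying a peel-safety rule to the peel is logical and does not by itself show an oversight. The UV and contraception intervals serve other purposes, so they are weak evidence of inconsistency. The investigator can also refuse a recent stopper under inclusion 5, and the lesion minimum in inclusion 6 limits entry of subjects who are still well suppressed. All of this stands. However, the investigator's gate is discretionary, exclusion 8 is worded for treatment being received, and inclusion 8 does not look back before D0.

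The strongest objection is that no harm is shown. Nothing in the documents says that 14 to 16 days is too short for any named treatment, or that 30 days is long enough for counts to settle; the 30 days were chosen for over-peeling. This stands too, and it keeps the point at low priority.

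A further objection is that the plan already has a useful count. At V2 the lesion count is listed before the peel (section 6.4.1.2), and by then every compliant subject is at least 30 days off treatment. The D0-to-D15 change can therefore be examined. But the accompanying cosmetics are handed out at D0, including a 15% glycolic acid foamer and a night cream (section 6.2.2). D15 therefore follows two weeks of their use and cannot stand in for a clean baseline.

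A reader might infer that baseline has no fixed protection at all. That is not so: exclusion 9 and the visit schedule together guarantee 14 to 16 days. A reader might also infer a bias in favour of the device. The documents do not support that. If an earlier treatment benefit wanes after D0, later counts rise and the effect is understated.

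**Conclusion.** The point holds as a minor design weakness. The plan's own rule and schedule leave an implied 14 to 16 days, rather than 30, between stopping acne treatment and the count on which the primary result rests. This follows from the documents alone and needs no outside assumption.

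The consequence is less certain. It requires that some recent stoppers are enrolled and that their counts are still drifting after D0, and the documents establish neither. The 0.07 to 0.83 lesion range rests entirely on the assumed 1 to 5 subjects and 2 to 5 lesions; it shows scale and is not an estimate. No direction of bias is claimed. The change is worth making because an uncontrolled change-from-baseline study cannot correct for such drift afterwards, and because the amendment is small.

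**What to change.** Reword exclusion 9, in section 6.3.2 and in the synopsis, so that topical or oral acne treatment must have stopped at least 30 days before the D0 lesion count. Record the stop date of prior acne treatment in the eCRF. Section 6.2.3.1 already captures start and stop dates for concomitant treatments, so this is a clarification of data capture. Eligibility on this criterion is then settled at entry. The sponsor should confirm that 30 days is adequate for stable counts, since the figure is the plan's own and was set for another purpose.

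If the criterion is kept, add one sensitivity analysis of the primary endpoint that omits subjects less than 30 days off treatment at D0. Also describe the D0-to-D15 pre-peel change in those subjects, noting the two weeks of accompanying cosmetics.

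The rewording changes neither the sample size nor the model. Its cost is the longer wait for recent stoppers. Because enrolment plus follow-up already fills the planned duration, those found late in enrolment may be lost rather than delayed. Phone pre-selection (section 6.3.5) allows D0 to be booked after the interval for those found earlier. The fallback costs no enrolment time, only the modest loss of precision shown in the working.
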